7.2.2.2 Vital signs

Vital signs include body temperature, respiratory rate, blood pressure and pulse measurements. Vital signs should be taken before any study medication is given on each assessment day (i.e. pre-dose).

Blood pressure will be taken:

- After the patient has rested for at least 3 minutes. The appropriate cuff size must be used to ensure accurate measurement
- Measurements will be taken per local practice

If the blood pressure reading is outside the age appropriate normal ranges, repeat the measurement, waiting 1-2 minutes between readings, to verify the initial reading. Repeat measurements will be documented in the eCRF.

7.2.2.3 Height and weight

Height in centimeters (cm) will be measured at screening according to [Table 7-1](#).

Body weight (to the nearest 0.1 kilogram [kg], in indoor clothing, but without shoes) will be measured at screening and at subsequent time points as specified in [Table 7-1](#) and [Table 7-2](#).

7.2.2.4 ECOG performance status

The Eastern Cooperative Oncology Group (ECOG) performance status scale will be used as described in the [Table 7-1](#).

7.2.2.5 Laboratory evaluations

Clinical laboratory analyses managed by central laboratory are detailed in the [Table 7-3](#) for the first 6 months only. All other analysis required in the VES for first 6 months and analysis done during the additional 18 months follow-up (responders only) as per standard of care will be managed by local laboratory and are detailed in [Table 7-4](#) and [Table 7-5](#).

At any time during the study, abnormal laboratory parameters which are clinically significant and require an action to be taken with study treatment (e.g., require dose modification and/or interruption of study treatment, lead to clinical symptoms or signs, or require therapeutic intervention), whether specifically requested in the protocol or not, will be recorded on the AE eCRF page.

A central laboratory will be used for analysis of listed specimens collected in the first 6 months of the study. Details on the collections, shipment of samples and reporting of results by the central laboratory are provided to investigators in the laboratory manual.

Table 7-3 Clinical laboratory parameters collection plan for central lab (first 6 months)

Test Category	Test Name
Hematology	Hematocrit, Hemoglobin, MCH, MCHC, MCV, Platelets, Red blood cells, White blood cells, RBC Morphology, Differential (absolute and percentages)(Basophils, Eosinophils, Lymphocytes, Monocytes, Neutrophils and Other), Reticulocytes, and a Peripheral blood smear
Folate/B12 panel	Serum folate, Vitamin B12 (cobalamin)
Viral serologies included Hepatitis markers	Hepatitis A, B, C, human immunodeficiency virus (HIV), Herpes simplex virus (HSV), Epstein Barr virus (EBV), and cytomegalovirus (CMV) HBV-DNA, HbsAg, HbsAb, HbcAb, HCV RNA-PCR (baseline)
Chemistry	Albumin, Alkaline phosphatase, ALT, AST, Gamma-glutamyl-transferase (GGT), Lactate dehydrogenase (LDH), Bicarbonate, Calcium, Magnesium, Phosphorus, Chloride, Sodium, Potassium, Creatinine, Creatine kinase, Direct Bilirubin, Indirect Bilirubin, Total Bilirubin, Total Cholesterol, LDL, HDL, Total Protein, Triglycerides, Blood Urea Nitrogen (BUN) or Urea, Uric Acid Amylase, Lipase, Glucose (fasting)
Urinalysis	Microscopic Panel (Red Blood Cells, White Blood Cells, Casts, Crystals, Bacteria, Epithelial cells) Macroscopic Panel (Color, Bilirubin, Blood, Glucose, Ketones, Leukocytes esterase, Nitrite, pH, Protein, Specific Gravity, Urobilinogen)
Coagulation	Prothrombin time (PT), International normalized ratio [INR], Activated partial thromboplastin time (APTT)
Thyroid	T3 [free], T4 [free], TSH
Flow cytometry	CD4, CD3, CD8, CD19, CD16+56, CD3+4+8, CD4/CD8 Ratio, CD3/CD19 Ratio, peripheral blood GPI-deficient cells (absolute value preferred, %s are acceptable)
Additional tests	Urine free cortisol (UFC), Insulin-like growth factor 1 (IGF-1), Alpha fetoprotein (AFP), Fractionated Alkaline Phosphatase, Testosterone (total and free), LH, FSH and SHBG

Test Category	Test Name
Pregnancy Test	When effective contraception is required pregnancy testing is mandated at screening and/or pre-dose and at the end of the study. A serum pregnancy test should be performed in part 1, while during the part 2 as per SOC and at the end of study urinary pregnancy tests are sufficient.

Table 7-4 Clinical laboratory parameters collection plan for local lab (first 6 months)

Test Category	Test Name
Blood type & screen	ABO and RhD typing, screening serum for atypical antibodies using 2-3 reagent screen cells
HLA type	Oligotyping, sequence-based typing (if not already available)
Cyclosporine	Cyclosporine through level

Table 7-5 Clinical laboratory parameters potentially collected as per local standard of care during the 18-months follow-up – Responders only

Test Category	Test Name
Hematology	Hematocrit, Hemoglobin, MCH, MCHC, MCV, Platelets, Red blood cells, White blood cells, RBC Morphology, Differential (Basophils, Eosinophils, Lymphocytes, Monocytes, Neutrophils), Bands, Reticulocytes, and a Peripheral blood smear
Folate/B12 panel	Serum folate, Vitamin B12 (cobalamin)
Chemistry	Albumin, Alkaline phosphatase, ALT, AST, Gamma-glutamyl-transferase (GGT), Lactate dehydrogenase (LDH), Bicarbonate, Calcium, Magnesium, Phosphorus, Chloride, Sodium, Potassium, Creatinine, Direct Bilirubin, Indirect Bilirubin, Total Bilirubin, Total Cholesterol, LDL, HDL, Total Protein, Triglycerides, Blood Urea Nitrogen (BUN) or Urea, Uric Acid Amylase, Lipase, Glucose (fasting)
Coagulation	Prothrombin time (PT), International normalized ratio [INR]
Thyroid	T3 [free], T4 [free], TSH
Cyclosporine	Cyclosporine through level
Flow cytometry	CD4, CD3, CD8, CD19, CD16+56, CD3+4+8, CD4/CD8 Ratio, CD3/CD19 Ratio, peripheral blood GPI-deficient cells (absolute value preferred, %s are acceptable)
Additional tests	Insulin-like growth factor 1 (IGF-1), Alpha fetoprotein (AFP), Testosterone (total and free), LH, FSH and SHBG
Pregnancy Test	A pregnancy test should be performed during cyclosporine administration as per local standard of care

7.2.2.5.1 Hematology

Hematology tests are to be performed by the central laboratory till first six months according to the schedule of assessments and collection plan outline, respectively, in [Table 7-1](#), [Table 7-2](#) and [Table 7-3](#). And then after 6 months (responders only) the hematology tests will be performed locally, as a minimum the 4 efficacy parameters (absolute neutrophil count, platelet count, reticulocyte count, hemoglobin) must be reported at each scheduled visit.

Reticulocyte count

Reticulocyte count is to be performed by the central laboratory till first six months according to the schedule of assessments and collection plan outline, respectively, in [Table 7-1](#), [Table 7-2](#) and [Table 7-3](#). And then after 6 months the reticulocyte count will be performed locally.

Blood type & screen

Blood typing and screening is to be performed by the local laboratory at screening, if results are not already available in patient chart according to the schedule of assessments and collection plan outline, respectively, in [Table 7-1](#) and [Table 7-4](#).

Coagulation

Coagulation tests are to be performed at baseline by the central laboratory according to the schedule of assessments and collection plan outlined respectively in [Table 7-1](#), [Table 7-3](#) and [Table 7-5](#).

Peripheral blood cytometry for GPI-deficient cells

Peripheral blood cytometry for the presence of GPI-deficient cells diagnostic of PNH will be performed by the central laboratory at baseline, at 3 months and at 6 months and according to the schedule of assessments and collection plan outline, respectively, in [Table 7-1](#), [Table 7-2](#) and [Table 7-3](#). And then after 6 months (responders only) the peripheral blood cytometry will be performed locally at 12 months and at 24 months.

7.2.2.5.2 Clinical chemistry

Chemistry testing is to be performed by the central laboratory at every visit till first six months according to the schedule of assessments and collection plan outline, respectively, in [Table 7-1](#), [Table 7-2](#) and [Table 7-3](#). And then after 6 months chemistry testing will be performed locally at each proposed visit.

Folate/B12 panel

Serum folate and vitamin B12 are to be performed by the central laboratory at baseline and at month 6 according to the schedule of assessments and collection plan outline, respectively, in [Table 7-1](#), [Table 7-2](#) and [Table 7-3](#).

HLA typing

Human leukocyte antigen typing is to be performed by the local laboratory, if results are not already available in patient chart, as per standard of care. These results will be collected at baseline according to the schedule of assessments and collection plan outline, respectively, in [Table 7-1](#).

Viral serologies

Viral serology testing is to be performed by the central laboratory at screening according to the schedule of assessments and collection plan outline, respectively, in [Table 7-1](#).

Thyroid test

T3 [free], T4 [free], TSH will be measured according to the schedule of assessments and collection plan outline, respectively, in [Table 7-1](#) and [Table 7-2](#).

Additional tests

Urine free cortisol (UFC), Insulin-like growth factor 1 (IGF-1), Alpha fetoprotein (AFP), Fractionated Alkaline Phosphatase, Testosterone (total and free), LH, FSH and SHBG will be measured according to the schedule of assessments and collection plan outline, respectively, in [Table 7-1](#) and [Table 7-2](#).

7.2.2.5.3 Urinalysis

Macroscopic urine panel for specific gravity, protein, glucose and blood will be performed at baseline and 6 months according to the schedule of assessments and collection plan outlined respectively in [Table 7-1](#) and [Table 7-3](#). Any significant findings on macroscopic urine panel will be followed up with a microscopic evaluation.

7.2.2.5.4 Pregnancy and assessments of fertility

Females of child-bearing potential are defined as all females physiologically capable of becoming pregnant. This includes female children and adolescents who are post-menarche or who experience menarche during the study. Pregnancy test will be performed for all females of child-bearing potential at baseline according to the schedule in [Table 7-1](#) and [Table 7-2](#).

Serum pregnancy test is required at screening and monthly until the end of treatment of eltrombopag and cyclosporine or the end of the study (depending upon the reason why the patient discontinued study medication). During the additional 18 months follow-up (responders only) of the study, it is highly recommended to perform the pregnancy test on monthly basis but the SOC can be also followed at the discretion of the investigator practice. Urine or serum pregnancy testing will be repeated approximately every 4 weeks while receiving study drug until study drug discontinuation. A serum pregnancy test may be used to confirm the results of a urine pregnancy test. Additional pregnancy tests may be performed at the investigator's discretion during the study. Additional pregnancy tests may be performed at the investigator's discretion during the study. Patients becoming pregnant must be discontinued from study drug.

Females of child-bearing potential who are or might become sexually active, must be informed of the potential teratogenic risk with eltrombopag and cyclosporine and the need for highly effective contraception to prevent pregnancy while on eltrombopag and cyclosporine therapy:

Use of oral, injected or implanted hormonal methods of contraception or placement of an intrauterine device (IUD) or intrauterine system (IUS) or other forms of hormonal contraception that have comparable efficacy (failure rate < 1%), for example hormone vaginal ring or transdermal hormone contraception.

Contraception must be used during the study and for 3 months after stopping treatment. The decision on the contraceptive method should be reviewed at least every 3 months to evaluate the individual need and compatibility of the method chosen.

Sexually active male patients, if they don't agree to abstinence, must use agree to use of highly effective methods of contraception as outlined in the Inclusion Criteria while taking study drugs and for 3 months after stopping treatment, and should not father a child during this period.

7.2.2.6 Bone marrow assessments

Bone marrow aspirate and biopsies, for cellularity and cytogenetics, morphology, degree of fibrosis, collagen, dysplasia, [REDACTED] will be sampled during Screening, 6 months and 12 months after start of study treatment according to the schedule of assessments and collection plan outlined respectively in [Table 7-1](#), [Table 7-2](#) and [Table 7-7](#).

The bone marrow aspirate and biopsy must be taken during the first days of the screening period [REDACTED] and sent for central review to determine patient's eligibility for enrollment and the results will be used as baseline value.

If local archival bone marrow biopsy sample within 2 months prior to screening is available, it may be sent for central review at screening if stored according to standard bone marrow sampling and archival process at site, although new biopsy sample is encouraged. However, bone marrow aspirate sample must be taken at screening and sent for central review.

If central laboratory is unable to perform the test (i.e., due to quality/sampling issue with the sample), particularly for cellularity and chromosome abnormality, the site may send one more bone marrow sample as soon as possible to central laboratory (re-screen the patient).

Bone marrow findings will be recorded and will be correlated with hematological samples.

7.2.2.7 Radiological examinations

Radiological examinations (computed tomography, chest x-ray) may be performed at screening and during the study at the discretion of the Investigator.

7.2.2.8 Cardiac assessments

7.2.2.8.1 Electrocardiogram (ECG)

A standard 12 lead ECG will be performed as per the assessment plan in [Table 7-1](#), [Table 7-2](#) and [Table 7-6](#).

Table 7-6 Local ECG collection plan

Visit	Day	Time	ECG Type
Screening	1	Pre-dose	12 Lead, triplicate
D1	1	Pre-dose	12 Lead, triplicate
Week 26 (6M) or EOT eltrombopag	1	Pre-dose	12 Lead, triplicate
Week 53 (1Y)*	1	Pre-dose	12 Lead, triplicate
Month 24 (2Y) or EOT cyclosporine*	1	Pre-dose	12 Lead, triplicate
Unscheduled sample		Anytime	12 Lead, triplicate

*only for responders.

Interpretation of the tracing must be made by a qualified physician and documented on the ECG eCRF page. Each ECG tracing should be labeled with the study number, patient initials (where

regulations permit), patient number, date, and kept in the source documents at the study site. Clinically significant findings must be discussed with Novartis prior to enrolling the patient in the study.

TriPLICATE ECG must be performed, the individual ECGs must be recorded approximately 2 minutes apart. The mean QTcF value for each visit must be calculated from the triplicate ECGs for each patient.

Additional, unscheduled, safety ECGs may be repeated at the discretion of the investigator at any time during the study as clinically indicated. Unscheduled ECGs with clinically significant findings should be collected in triplicate. Local cardiologist ECG assessment may also be performed at any time during the study at the discretion of the investigator.

Clinically significant ECG abnormalities present at screening should be reported on the Medical History eCRF page. New or worsened clinically significant findings occurring after informed consent must be recorded on the Adverse Events eCRF page.

7.2.2.8.2 Cardiac imaging - MRA (magnetic resonance angiography), MUGA (multiple gated acquisition) scan or echocardiogram

Not applicable.

7.2.2.8.3 Cardiac enzymes

CK will be assessed at each landmark visits 3, 6, 12* and 24*.

*Only for responders.

7.2.2.9 Tolerability

Not applicable.

7.2.3 Pharmacokinetics

Blood samples for eltrombopag pharmacokinetic (PK) evaluation will be collected from all patients who receive at least one dose of eltrombopag.

Blood sampling for PK will be performed as indicated in the Visit Evaluation Schedule ([Table 7-1](#)). Sampling time points for the study of eltrombopag PK are detailed in [Table 7-7](#).

Table 7-7 Pharmacokinetic blood collection log (eltrombopag)

PK Sample #	PK collection # dose reference ID (DRID)	Study week	Scheduled time point (hours post-dose)
1	1 ^a /101 ^b	2	Pre-dose ^{a, d} /0 hr
2	1	2	2 (± 15 min)
3	1	2	4 (± 30 min)
4	1	2	6 (± 30min)
5	1	2	8 (± 30min)
7	2 ^a /102 ^b	4	Pre-dose ^a /0 hr
8	3 ^a /103 ^b	8	Pre-dose ^a /0 hr
9	4 ^a /104 ^b	12	Pre-dose ^a /0-hr
10	5 ^a /105 ^b	26	Pre-dose ^a /0-hr

PK Sample #	PK collection # dose reference ID (DRID)	Study week	Scheduled time point (hours post-dose)
1001, 1002, etc.	Unscheduled	Unscheduled	Unscheduled ^c

* NOTE: One single blood draw will be obtained from each patient at each time point. PK collection # dose reference Id (DRID) is only for Novartis internal use.

a. Collect PK sample immediately before drug administration.

b. Dose reference ID number to collect last dose information.

c. Unscheduled PK blood samples may be collected at any time for measurement of plasma drug concentrations if clinically indicated or at the Investigator's discretion and will be uniquely, sequentially numbered 1001, 1002, etc.

d. Data from this pre-dose sample will be duplicated during the PK merge and will be attributed a different sample number in order to also be analyzed as a 24 h post-dose sample.

Vomiting information after administration will be collected within 4 hours of dosing.

In case of DILI (see [Section 6.3.1.1](#)), an unscheduled eltrombopag PK sample should be collected.

On the days of PK collection, the patient will be advised to take study drug after the pre-dose blood sample is taken.

[figure not shown]
Patients who receive blood transfusions during the weeks leading up to the maximum tolerated dose, will still have PK samples taken but will be identified as such in the PK analyses.

7.2.3.1 Analytical method

The plasma samples from all patients will be assayed for eltrombopag concentrations using a validated liquid chromatography – tandem mass spectrometry assay (LC-MS/MS). The lower limit of quantitation (LLOQ) will be 100 ng/mL.

Concentration values below the LLOQ will be reported as zero, and missing samples will be labeled accordingly. Further refinements of these bioanalytical methods may be conducted during the course of the study.

All relevant information will be provided in the [CETB115E2403 Laboratory Manual].

7.2.5 Resource utilization

Not Applicable.

7.2.6 Patient reported outcomes

Patients with SAA often present with significant symptoms that interfere with their health related quality of life including, fatigue, difficulty breathing on exertion, easy bruising, epistaxis, petechiae and gingival bleeding. The effect of eltrombopag on patient symptoms will be measured using several assessment tools including Eastern Cooperative Oncology Group (ECOG) performance status, the FACIT-fatigue, the FACT-TH18 (includes FACT-G) [REDACTED]

[REDACTED] All questionnaires, except the ECOG performance status, which is completed by the treating physician, are electronic patient reported outcomes (ePRO): these questionnaires will be completed on a tablet by the patient.

Instructions for all ePROs will be provided as separate documents: Patients must complete the questionnaires before other clinical assessments at any given visit. The ePRO questionnaires should be completed in the same order at each visit to ensure that the patient is answering them as consistently as possible. The questionnaires should be given in the following order:

1. FACIT-Fatigue
2. FACT-TH18

[REDACTED]
Questionnaires will be collected according to the Visit Schedule outlines in [Table 7-1](#), and [Table 7-2](#).

The patient should be given sufficient space and time to complete the ePRO questionnaires. The site personnel should check the questionnaires for completeness and ask the patient to complete any missing responses. The original questionnaire will be kept with the patient's file as the source document.

Completed questionnaires and any unsolicited comments provided by the patient should be assessed by the investigator which may indicate potential AEs or SAEs before any clinical study examination. This assessment should be documented in study source records. If AEs or SAEs are confirmed, study investigators should not encourage the patient to change responses reported in the completed questionnaires. Study investigators must follow reporting instruction outlines in [Section 8](#) (e.g. reference "Adverse Event" section) of the study protocol.

The FACIT-Fatigue

The FACIT- Fatigue is a 13-items fatigue subscale that asks the patient to rate their degree of tiredness, weakness and fatigue. All items of the FACIT-Fatigue use a 5 point scale ranging from 0 to 4 with a 0 rating being "not at all" and a 4 rating being "very much".

Total score ranges from 0 to 52. Negatively worded items are reverse scored prior to summing so that higher total scores indicate less fatigue.

[figure not shown]
The FACT-TH18 is comprised of the FACT-G and a thrombocytopenia specific questionnaire.

The FACT-G consists of 27-items divided into four QOL domains:

- Physical Well-Being
- Social/Family Well-Being
- Emotional Well-Being
- Functional Well-Being

The FACT-TH18 has 18-items which asks the patient to rate their degree of thrombocytopenia.

All items of the FACT-TH18 use a 5 point scale ranging from 0 to 4 with a 0 rating being “not at all” and a 4 rating being “very much”.

8 Safety monitoring and reporting

8.1 Adverse events

8.1.1 Definitions and reporting

An adverse event is defined as the appearance of (or worsening of any pre-existing) undesirable sign(s), symptom(s), or medical condition(s) that occur after patient’s signed informed consent has been obtained.

Abnormal laboratory values or test results occurring after informed consent constitute adverse events only if they induce clinical signs or symptoms, are considered clinically significant, require therapy (e.g., hematologic abnormality that requires transfusion or hematological stem cell support), or require changes in study medication(s).

Adverse events that begin or worsen after informed consent should be recorded in the Adverse Events eCRF. Conditions that were already present at the time of informed consent should be recorded in the Medical History page of the patient’s eCRF. Adverse event monitoring should be continued for at least 30 days (or 5 half-lives, whichever is longer) following the last dose of study treatment. Adverse events (including lab abnormalities that constitute AEs) should be described using a diagnosis whenever possible, rather than individual underlying signs and symptoms. When a clear diagnosis cannot be identified, each sign or symptom should be reported as a separate adverse event.

Adverse events will be assessed and graded according to the Common Terminology Criteria for adverse events (CTCAE) version 4.03. Grade 1 to 5 will be used to characterize the severity of the adverse event.

If CTCAE grading does not exist for an adverse event, the severity of mild, moderate, severe, and life-threatening, death related to the AE corresponding respectively to Grades 1 - 5, will be used. Information about any deaths (related to an adverse event or not) will also be collected through a Death form.

The occurrence of adverse events should be sought by non-directive questioning of the patient (subject) during the screening process after signing informed consent and at each visit during the study. Adverse events also may be detected when they are volunteered by the patient (subject) during the screening process or between visits, or through physical examination, laboratory test, or other assessments. As far as possible, each adverse event should be evaluated to determine:

1. The severity grade (CTCAE Grade 1-5)
2. Its duration (Start and end dates)
3. Its relationship to the study treatment (Reasonable possibility that AE is related: No, Yes)
4. Action taken with respect to study treatment (none, dose adjusted, temporarily interrupted, permanently discontinued, unknown, not applicable)
5. Whether medication or therapy was given (no concomitant medication/non-drug therapy, concomitant medication/non-drug therapy)
6. Whether it is serious, where a Serious Adverse Event (SAE) is defined as in Section 8.2.1 and which seriousness criteria have been met
7. Outcome (not recovered/not resolved, recovered/resolved, recovering/resolving, recovered/resolved with sequelae, fatal, unknown)

If the event worsens the event should be reported a second time in the eCRF noting the start date when the event worsens in toxicity. For grade 3 and 4 adverse events only, if improvement to a lower grade is determined a new entry for this event should be reported in the eCRF noting the start date when the event improved from having been Grade 3 or Grade 4.

All adverse events should be treated appropriately. If a concomitant medication or non-drug therapy is given, this action should be recorded on the Adverse Event eCRF.

Once an adverse event is detected, it should be followed until its resolution or until it is judged to be permanent, and assessment should be made at each visit (or more frequently, if necessary) of any changes in severity, the suspected relationship to the study treatment, the interventions required to treat it, and the outcome.

Progression of malignancy (including fatal outcomes), if documented by use of appropriate method (for example, as per RECIST criteria for solid tumors or as per Cheson's guidelines for hematological malignancies), should not be reported as a serious adverse event.

Adverse events separate from the progression of malignancy (example, deep vein thrombosis at the time of progression or hemoptysis concurrent with finding of disease progression) will

be reported as per usual guidelines used for such events with proper attribution regarding relatedness to the drug.

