10.5.3.2 Adverse events (AEs)

Summary tables for Adverse Events (AEs) will include only AEs that started or worsened during the on-treatment period, the ***treatment-emergent*** AEs.

The incidence of treatment-emergent AEs (new or worsening from baseline) will be summarized by system organ class and or preferred term, severity (based on CTCAE grades), type of AE, relation to study treatment

Serious adverse events, non-serious AEs and AEs of special interest (*AESI*) during the on-treatment period will be tabulated.

All deaths (on-treatment and post-treatment) will be summarized.

All AEs, deaths and SAEs (including those from the pre and post-treatment periods) will be listed and those collected during the pre-treatment and post-treatment period will be flagged.

Project-specific AESIs should be defined in the case retrieval strategy (CRS) with regular updates whenever necessary, see also Section 8.1.3.

AEs will be coded using the latest MedDRA terminology version during the time of data analyses.

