The reference start date for all assessments (safety, efficacy, patient reported outcomes (PROs), etc.) will be the start date of study treatment.

The study day will be displayed in the data listings. If an event starts before the reference start date, the study day displayed in the listing will be negative.

Baseline

Baseline is the result of an investigation describing the “true” uninfluenced state of the patient, defined as the period from the date of signing any informed consent document to the start date of study treatment. Assessments, specified to be collected post-dose on the first date of study treatment are not considered.

The last non-missing assessment, including unscheduled assessments on or before the date of start of study treatment is defined as “baseline value” or “baseline assessment”.

Where multiple measurements meet the baseline definition, with no further flag or label that can identify the chronological order, then values from central assessments should be considered as baseline rather than local values.

For electrocardiogram (ECG) parameters, if there are multiple replicates per time point, the average of these measurements would be calculated for baseline (if not already available in the database).

If patients have no value as defined above, the baseline result will be missing.

Observation periods

The overall observation period will be divided into three mutually exclusive segments:

1. **Pre-treatment:** from day of patient’s informed consent to start date of study treatment
2. **On-treatment:** from start date study treatment to last date of study treatment + 30 days
3. **Post-treatment:** from last date of study treatment + 31 days

On-treatment assessments/events

The definition of on-treatment is given below, depending on the context.

For safety summary tables an on-treatment AE is defined as any AE reported in the following time interval (including the lower and upper limits):

- <date of first administration of study treatment; date of last administration of study treatment + 30 days>

This corresponds to the definition of treatment-emergent AEs given in the protocol, i.e. AEs which are newly reported or worsening from baseline.

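### The SAP's date-only rule for on-treatment AEs can count the improvement of a pre-dose Grade 3-4 event as treatment-emergent, contrary to the protocol's definition

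*Protocol*

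**What the plan says.** Four provisions meet here.

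- **What reaches the AE form before dosing.** Protocol 8.1.1: "Adverse events that begin or worsen after informed consent should be recorded in the Adverse Events eCRF". Screening may start up to 21 days before treatment (protocol 7.1.2), so AE records dated before first dose can exist. Anything older goes elsewhere: "Conditions that were already present at the time of informed consent should be recorded in the Medical History page".
- **When a second record is opened.** Protocol 8.1.1 covers both directions. For worsening: "If the event worsens the event should be reported a second time in the eCRF noting the start date when the event worsens in toxicity". Easing also opens one, but only where the event was at Grade 3 or 4: "if improvement to a lower grade is determined a new entry for this event should be reported in the eCRF noting the start date".
- **What the protocol wants tabulated.** Protocol 10.5.3.2: "Summary tables for Adverse Events (AEs) will include only AEs that started or worsened during the on-treatment period". It repeats the idea when defining the summaries: "The incidence of treatment-emergent AEs (new or worsening from baseline) will be summarized".
- **What the SAP does.** SAP 2.1.3: "For safety summary tables an on-treatment AE is defined as any AE reported in the following time interval". The interval runs from first dose to last dose plus 30 days, both ends included. The SAP then states that this agrees with the protocol's treatment-emergent definition. SAP 2.7.1 tabulates on-treatment AEs and, where a patient has several under one preferred term, shows the most severe.

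**The concern.** On this form a start date after first dose does not show whether an event began, worsened or improved, because all three produce a record with such a date. A rule that looks only at dates therefore cannot separate the first two, which the protocol wants counted, from the third, which it does not.

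At stake is the meaning of the treatment-emergent tables. A patient whose pre-dose event got better on treatment could appear as having acquired an adverse event on treatment. The error runs one way, since this mechanism can only add entries. The trial has a single arm, so there is no control column in which a reader could see the same effect.

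**Working it through.** The documents give no figure to reproduce; the check is a comparison of rules. Let F be the date of first dose and L the date of last dose, so that the SAP interval is F to L + 30 days.

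| Course of the event | Records under protocol 8.1.1 | Inside F to L + 30? | Counted under SAP 2.1.3 read literally | Counted under protocol 10.5.3.2 |
|---|---|---|---|---|
| Present at consent, no later worsening | Medical History only | No AE record | No | No |
| Starts after F at Grade 3-4, then eases | Original and improvement | Both | Yes, once, at the worse grade | Yes |
| Starts between consent and F, worsens after F | Original and worsening | Second only | Yes | Yes |
| Starts between consent and F at Grade 1-2, eases after F | Original only | No | No | No |
| Starts or worsens to Grade 3-4 between consent and F, eases to a lower grade after F | Worse record and improvement | Improvement only | **Yes** | **No** |

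Only the last row disagrees. No later step in the SAP repairs it:

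- The greatest-severity rule in SAP 2.7.1 works among on-treatment records, so the worse pre-dose record is not available for comparison.
- SAP 2.1.3 defines baseline for assessments. It defines no baseline grade for an adverse event.
- Neither document links an improvement record to the record it continues.

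The grade shown would be the improved one. Entry to the optional Grade 3 or higher column therefore needs a fall from Grade 4 to Grade 3. Falls from 4 to 2 or 1, or from 3 to 2 or 1, affect only the all-grades column.

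**Size.** SAP section 1 gives 54 enrolled patients. I take all 54 as dosed. If k patients follow the last row for one preferred term, and none has another on-treatment record of that term, the row rises by k/54:

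- k = 1: 1/54 = 1.9 percentage points
- k = 3: 3/54 = 5.6 percentage points
- k = 5: 5/54 = 9.3 percentage points

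These values of k are assumptions to show scale; the documents give no count. Each result is a maximum: a patient who has the same term again on treatment would be in the row anyway. In columns split by responder status, age or ethnicity the denominator is smaller and each step larger, but those group sizes are not given.

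**The case against.** The best defence is that the stated definition already excludes these records. Protocol 8.1.1 treats the improvement record as part of the same event, which started before dosing. Protocol 10.5.3.2 limits the tables to events that began or worsened on treatment, and the SAP ties its interval to that idea. Variable derivations sit in the programming data specifications (SAP section 1), a separate document that may contain the missing filter. This stands in part: one cannot say that the tables contain the error. It does not rescue the rule. The SAP presents the interval as already equivalent to the definition, which gives a programmer no reason to add a filter. Its restatement of the definition, in terms of new reports, is also ambiguous when the form calls the improvement record new.

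A reader might infer that the problem is common here, because patients enter with severe cytopenias and one death occurred in screening. Neither fact supports that. Cytopenias present at consent belong in Medical History and open no AE improvement record unless they worsened as adverse events before first dose. A patient who died without being dosed is a screen failure, lies outside the Safety Set, and cannot improve after first dose.

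The group is narrow in other ways too. The patient must have a Grade 3-4 event arising or worsening in a short pre-dose period, remain eligible, be dosed, and then pass through a lower grade. Current eligibility excludes inadequately controlled infection, severe concurrent disease and ECOG status of 2 or more, although some of these limits came with Amendment 2, when 31 patients had been enrolled.

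Finally, all AEs are listed and those outside the treatment period flagged, so the worse record stays visible in the listings. That helps a reviewer who looks for it, but does not correct a table.

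**Conclusion.** The point holds as a misstated rule with a probably small effect. SAP 2.1.3 claims an equivalence with the protocol's treatment-emergent definition that its date interval does not deliver, because protocol 8.1.1 dates improvements as well as onsets and worsenings. Applied literally, it counts some improving pre-dose events.

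The effect in the all-patient column is at most 1.9 percentage points per affected patient and preferred term, always upward. The overall any-AE row moves only for a patient with no other on-treatment AE, which is unlikely over six months of weekly and then two-weekly visits. An effect on the SAE table would require the improvement record to carry the serious flag, which the documents do not settle.

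Two stronger conclusions are not supported: that the tables are known to be wrong, since the programming specifications are not available; and any stated number of affected patients, since the documents give no count of Grade 3-4 events between consent and first dose.

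**What to change.** Add to SAP 2.1.3: an AE record that continues an event which started before first dose is treatment-emergent only if its grade exceeds the last pre-dose grade of that event. Otherwise it is listed and flagged, and left out of the AE, SAE, AESI and Grade 3 or higher summaries. Remove the statement that the date interval alone corresponds to the protocol definition.

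The cost is one or two sentences in the SAP and a programming step that links records of the same event by preferred term and contiguous dates. Grades and dates are already collected, so no new data are needed, and the change brings the SAP into line with the existing protocol text.

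The downside is timing. The interim lock for the primary analysis was on 09-Dec-2020 and the primary CSR has been written. If the rule changes any count, the final tables will differ from the primary ones. The sponsor should check the primary tables for such records and explain any difference in a footnote to the final CSR.
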